12.10. Appendix 10: Liver Safety Drug Restart Guidelines

If subject meets liver chemistry stopping criteria do not restart randomized treatment unless there is a clear underlying cause for the liver stopping event other than drug-induced liver injury and:

- GSK Medical Governance approval **is granted** (as described below),
- Ethics and/or IRB approval is obtained, if required, and
- Separate consent for treatment restart is signed by the subject

If GSK Medical Governance approval to restart subject with randomized treatment **is not granted**, then subject must permanently discontinue randomized treatment and requested to continue in the study for protocol-specified follow up assessments.

Restart Following Transient Resolving Liver Stopping Events Not Related to Randomized Treatment

Restart refers to resuming randomized treatment following liver stopping events in which there is a clear underlying cause (other than DILI) of the liver event (e.g. biliary obstruction, pancreatic events, hypotension, acute viral hepatitis). Furthermore, there should be no evidence of alcoholic hepatitis or hypersensitivity, and the randomized treatment should not be associated with HLA markers of liver injury.

Approval by GSK for randomized treatment restart can be considered where:

- Investigator requests consideration for randomized treatment restart if liver chemistries have a clear underlying cause (e.g., biliary obstruction, hypotension and liver chemistries have improved to normal or are within 1.5 x baseline and ALT <3xULN).
- Restart risk factors (e.g. fever, rash, eosinophilia, or hypersensitivity, alcoholic hepatitis, possible randomized treatment-induced liver injury) or randomized treatment has an HLA genetic marker associated with liver injury (e.g. lapatinib, abacavir, amoxicillin/clavulanate) are reviewed and excluded.
- Ethics Committee or Institutional Review Board approval of randomized treatment restart must be obtained, as required.
- If restart of randomized treatment is approved by GSK Medical Governance in writing, the subject must be provided with a clear description of the possible benefits and risks of randomized treatment administration, including the possibility of recurrent, more severe liver injury or death.
- The subject must also provide signed informed consent specifically for the randomized treatment restart. Documentation of informed consent must be recorded in the study chart.
- Randomized treatment must be administered at the dose specified by GSK.
- Subjects approved by GSK Medical Governance for restarting randomized treatment must return to the clinic once a week for liver chemistry tests until

- stable liver chemistries have been demonstrated and then laboratory monitoring may resume as per protocol.
- If after randomized treatment re-start, subject meets protocol-defined liver chemistry stopping criteria, follow usual stopping criteria instructions.
 - PPD Medical Monitor, and the Ethics Committee or Institutional Review Board as required, must be informed of the subject's outcome following randomized treatment restart.
 - PPD to be notified of any AEs, as per Section 7.4 and [Appendix 8](#).

12.11. Appendix 11: Collection of Pregnancy Information

- Investigator will collect pregnancy information on any female subject who becomes pregnant while participating in this study.
- Information will be recorded on the appropriate form and submitted to PPD within 24 hours of learning of a subject's pregnancy.
- The subject will be followed to determine the outcome of the pregnancy. The investigator will collect follow up information on mother and infant, which will be forwarded to PPD. Generally, follow-up will not be required for longer than 6 to 8 weeks beyond the estimated delivery date.
- Any termination of pregnancy will be reported, regardless of fetal status (presence or absence of anomalies) or indication for procedure.
- While pregnancy itself is not considered to be an AE or SAE, any pregnancy complication or elective termination of a pregnancy will be reported as an AE or SAE.
- A spontaneous abortion is always considered to be an SAE and will be reported as such.
- Any SAE occurring as a result of a post-study pregnancy which is considered by the investigator reasonably related to the randomized treatment, will be reported to PPD as described in [Appendix 8](#). While the investigator is not obligated to actively seek this information in former study participants, he or she may learn of an SAE through spontaneous reporting.

Any female subject who becomes pregnant while participating must permanently discontinue randomized treatment. Subjects will be asked to attend an Early Treatment Discontinuation visit and expected to attend study visits through the End of Study visit, according to the study visit schedule, unless consent is actively withdrawn.

12.12. Appendix 12: Genetic Research

Genetics – Background

Naturally occurring genetic variation may contribute to inter-individual variability in response to medicines, as well as an individual's risk of developing specific diseases. Genetic factors associated with disease characteristics may also be associated with response to therapy, and could help to explain some clinical study outcomes. For example, genetic variants associated with age-related macular degeneration (AMD) are reported to account for much of the risk for the condition [Gorin, 2012] with certain variants reported to influence treatment response [Chen, 2012]. Thus, knowledge of the genetic etiology of disease may better inform understanding of disease and the development of medicines. Additionally, genetic variability may impact the pharmacokinetics (absorption, distribution, metabolism, and elimination), or pharmacodynamics (relationship between concentration and pharmacologic effects or the time course of pharmacologic effects) of a specific medicine and/or clinical outcomes (efficacy and/or safety) observed in a clinical study.

Genetic Research Objectives and Analyses

The objectives of the genetic research are to investigate the relationship between genetic variants and:

- Response to medicine, including any treatment regimens under investigation in this study or any concomitant medicines;
- Anemia associated with CKD susceptibility, severity, and progression and related conditions

Genetic data may be generated while the study is underway or following completion of the study. Genetic evaluations may include focused candidate gene approaches and/or examination of a large number of genetic variants throughout the genome (whole genome analyses). Genetic analyses will utilize data collected in the study and will be limited to understanding the objectives highlighted above. Analyses may be performed using data from multiple clinical studies to investigate these research objectives.

Appropriate descriptive and/or statistical analysis methods will be used. A detailed description of any planned analyses will be documented in a Reporting and Analysis Plan (RAP) prior to initiation of the analysis. Planned analyses and results of genetic investigations will be reported either as part of the clinical RAP and study report, or in a separate genetics RAP and report, as appropriate.

Study Population

Any subject who is randomized in the study can participate in genetic research. Any subject who has received an allogeneic bone marrow transplant must be excluded from the genetic research.

Study Assessments and Procedures

A key component of successful genetic research is the collection of samples during clinical studies. Collection of samples, even when no *a priori* hypothesis has been identified, may enable future genetic analyses to be conducted to help understand variability in disease and medicine response.

- A 6 ml blood sample will be taken for Deoxyribonucleic acid (DNA) extraction. A blood sample is collected at the Baseline visit, after the subject has been randomized and provided informed consent for genetic research. Instructions for collection and shipping of the genetic sample are described in the laboratory manual. The DNA from the blood sample may undergo quality control analyses to confirm the integrity of the sample. If there are concerns regarding the quality of the sample, then the sample may be destroyed. The blood sample is taken on a single occasion unless a duplicate sample is required due to an inability to utilize the original sample.

The genetic sample is labelled (or “coded”) with the same study specific number used to label other samples and data in the study. This number can be traced or linked back to the subject by the investigator or site staff. Coded samples do not carry personal identifiers (such as name or social security number).

Samples will be stored securely and may be kept for up to 15 years after the last subject completes the study, or GSK may destroy the samples sooner. GSK or those working with GSK (for example, other researchers) will only use samples collected from the study for the purpose stated in this protocol and in the informed consent form. Samples may be used as part of the development of a companion diagnostic to support the GSK medicinal product.

Subjects can request their sample to be destroyed at any time.

Informed Consent

Subjects who do not wish to participate in the genetic research may still participate in the study. Informed consent for genetic research must be obtained prior to any blood being taken.

Subject Withdrawal from Study

If a subject who has consented to participate in genetic research withdraws from the clinical study for any reason other than being lost to follow-up, the subject will be given a choice of one of the following options concerning the genetic sample, if already collected:

- Continue to participate in the genetic research in which case the genetic DNA sample is retained
- Discontinue participation in the genetic research and destroy the genetic DNA sample

If a subject withdraws consent for genetic research or requests sample destruction for any reason, the investigator must complete the appropriate documentation to request sample destruction within the timeframe specified by GSK and maintain the documentation in the site study records.

Genotype data may be generated during the study or after completion of the study and may be analyzed during the study or stored for future analysis.

- If a subject withdraws consent for genetic research and genotype data has not been analyzed, it will not be analyzed or used for future research.
- Genetic data that has been analyzed at the time of withdrawn consent will continue to be stored and used, as appropriate.

Screen and Baseline Failures

If a sample for genetic research has been collected and it is determined that the subject does not meet the entry criteria for participation in the study, then the investigator should instruct the subject that their genetic sample will be destroyed. No forms are required to complete this process as it will be completed as part of the consent and sample reconciliation process. In this instance a sample destruction form will not be available to include in the site files.

Provision of Study Results and Confidentiality of Subject's Genetic Data

GSK may summarize the genetic research results in the clinical study report, or separately and may publish the results in scientific journals.

GSK may share genetic research data with other scientists to further scientific understanding in alignment with the informed consent. GSK does not inform the subject, family members, insurers, or employers of individual genotyping results that are not known to be relevant to the subject's medical care at the time of the study, unless required by law. This is due to the fact that the information generated from genetic studies is generally preliminary in nature, and therefore the significance and scientific validity of the results are undetermined. Further, data generated in a research laboratory may not meet regulatory requirements for inclusion in clinical care.

References

Gorin MB. Genetic insights into age-related macular degeneration: Controversies addressing risk, causality, and therapeutics. *Mol. Asp. Med.* 2012; 33: 467-486.

12.13. Appendix 13: A Sub-study of the Effect of Daprodustat Compared to Darbepoetin Alfa on BP in Non-dialysis Subjects with Anemia Associated with CKD who are not Currently Using ESA Therapy

12.13.1. Introduction and Rationale

Hypertension is one of the major risk factors associated with cardiovascular morbidity and mortality and is common in patients with advanced CKD Stages 3b through 5.

Treatment of anemia associated with CKD using ESAs has the associated risk of increased BP, especially during the period of hemoglobin correction. ESA-induced elevation of BP often necessitates initiation of, or increases in, antihypertensive medications in patients with CKD. While SBP and DBP are both of prognostic importance, SBP is the overall best predictor of future cardiovascular risk in a hypertensive population [Peters, 2013]. Therefore, SBP was chosen as the primary endpoint in this ABPM sub-study. ABPM is being used to measure BP in this sub-study because previous studies have used this BP measurement modality in subjects with CKD to establish an association with mortality [Agarwal, 2010].

This sub-study is intended to compare daprodustat to darbepoetin alfa on BP as assessed by ABPM in ND subjects with anemia associated with CKD.

While multiple mechanisms likely underlie ESA-induced hypertension, reduced urinary sodium excretion is hypothesized to be a major mechanism by which ESAs potentiate hypertension and non-responsive BP dipping in patients with CKD [Krapf, 2009]. Patients with CKD may also excrete less urinary sodium since they have lower levels of renal nitric oxide (NO). Patients with CKD produce more reactive oxygen species that reduces NO, and NO normally stimulates urinary sodium excretion [Ge, 2006]. As daprodustat activates HIF signaling, and one of the downstream targets of HIF is nitric oxide synthase, daprodustat may augment urinary sodium excretion, reduce SBP and restore a responsive nocturnal BP dipping pattern. Therefore, in addition to comparing the effects of daprodustat to darbepoetin alfa on SBP in this sub-study, an exploratory objective is to compare urinary sodium and aldosterone excretion with daprodustat versus darbepoetin alfa, which may include excretion over 24 hrs or normalized to urinary creatinine.

12.13.2. Objectives and Endpoints

Objectives	Endpoints
Primary	

 To compare daprodustat to darbepoetin alfa for effect on SBP (superiority) by ABPM in ND subjects in the ABPM ITT population 	
 Change in 24 hour average SBP from baseline to end of sub-study¹ between treatment groups
Secondary	

 To assess the effect of daprodustat and darbepoetin alfa independently 	
 Change in 24 hour average SBP from baseline to end of sub-study¹ within each treatment group

Objectives	Endpoints
on SBP, DBP and mean arterial blood pressure (MAP) by ABPM in the ABPM ITT population	
 • Change in 24 hour average DBP from baseline to end of sub-study¹ within each treatment group • Change in 24 hour average MAP from baseline to end of sub-study¹ within each treatment group

 • To compare the effect of daprodustat to darbepoetin alfa on DBP and MAP by ABPM in the ABPM ITT population 	
 • Change in 24 hour average DBP from baseline to end of sub-study¹ between treatment groups • Change in 24 hour average MAP from baseline to end of sub-study¹ between treatment groups

 • To compare the effect of daprodustat to darbepoetin alfa on BP parameters in the ABPM per-protocol population 	
 • Change in 
 ○ 24 hour average SBP ○ 24 hour average DBP ○ 24 hour average mean arterial pressure from baseline to end of sub-study¹ between treatment groups

 • To compare daprodustat to darbepoetin alfa on BP parameters in the ABPM per-protocol population 	
 • Change in: 
 ○ 24 hour average SBP ○ 24 hour average DBP ○ 24 hour average mean arterial pressure from Baseline to end of sub-study¹ within each treatment group

 • To compare the percentage of subjects in each treatment group requiring a change in antihypertensive medications in the ABPM ITT population 	
 • Difference between treatment groups in percentage of subjects requiring no change in number or dosage of antihypertensive medications • Difference between treatment groups in percentage of subjects requiring an increase in number or dosage of antihypertensive medications • Difference between treatment groups in percentage of subjects requiring a decrease in number or dosage of antihypertensive medications

 • To characterize the dipping pattern of sleeping BP in each treatment group in the ABPM ITT and ABPM per-protocol populations 	
 • 24-hour BP profile as measured by ABPM, with subjects categorized according to their sleeping BP behaviors as: • dippers (normal) when the reduction in the average SBP during the sleeping period was >10% to 20% of mean SBP during waking hours, • extreme dippers when this reduction was >20%, • non-dippers when the reduction was <10%, and • reverse dippers when the mean sleep SBP was higher than the awake SBP [Bakris, 2014]

 • To compare the percentage of subjects that convert from non-dipper status to dipper status between treatment groups in the ABPM ITT and ABPM per-protocol populations 	
 • Difference between treatment groups in percentage of subjects that convert from non-dipper status at baseline to dipper status at end of sub-study¹

 • To compare the percentage of subjects that convert from dipper status to non-dipper status between treatment groups ABPM ITT and ABPM per-protocol populations 	
 • Difference between treatment groups in percentage of subjects that convert from dipper status at baseline to non-dipper status at end of sub-study¹

Objectives	Endpoints

 To compare the effect of treatment with daprodustat to darbepoetin alfa on heart rate by ABPM in the ABPM ITT population 	
 Change from baseline to end of sub-study¹ in 24 hour average heart rate between treatment groups as measured by ABPM relative to time since administration of medication
Exploratory	

 To compare urinary sodium excretion with daprodustat to darbepoetin alfa in the ABPM ITT population 	
 Difference between treatment groups in urinary sodium excretion from baseline to end of sub-study¹

 To compare the effect of treatment with daprodustat versus darbepoetin alfa on urinary aldosterone in the ABPM ITT population 	
 Difference between treatment groups in urinary aldosterone excretion from baseline to end of sub-study¹

1. . The end of the sub-study is defined as Week 16, or Week 28 for subjects completing the sub-study prior to Amendment 2.

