4. STUDY DESIGN

4.1. Overall Design

[figure not shown]
- This is a randomized, open-label (sponsor blind), active-controlled, parallel-group, multi-center, event-driven study in ND subjects with anemia associated with CKD.
- This study will comprise four study periods ([Figure 1](#)): a 4-week screening period, a 4-week placebo run-in period, a treatment period, and a follow-up period. Prior ESA² therapy, if present, continues during the screening and run-in periods.
- The treatment period consists of ([Figure 1](#)):
 - The stabilization period, defined as the period from Day 1 to Week 28 during which randomized treatment will be dose titrated to achieve the appropriate Hgb target.
 - The maintenance period, defined as the period from the end of the stabilization period (Week 28) to the end of treatment (variable per subject), to assess long term safety and efficacy.
 - The efficacy evaluation period (EP) is defined as the period from Week 28 to Week 52 during which Hgb efficacy will primarily be assessed.
- The total duration of the study is dependent upon the accumulation of 664 adjudicated first MACE (i.e., it is event-driven) unless review of interim data by the Independent Data Monitoring Committee (IDMC) recommends bringing the study to an earlier close.
- All subjects will remain in the study (including subjects that start dialysis or receive a kidney transplant), regardless of whether they continue with randomized treatment (unless consent for any further follow up is withdrawn), until the target number of first adjudicated MACE has occurred. At that point, the sponsor will notify investigators to have subjects come in for an End of Study visit within a pre-defined time period.
- The end of the study will occur after the accumulation of 664 adjudicated first MACE and the last subject has completed their last required study visit ([Section 7.1](#)).
- Subjects will be stratified by region (see [Appendix 3](#)), by whether they are currently using an ESA, and by participation in the ABPM sub-study. Region and ESA use at study entry are stratification factors considered to be potentially prognostically important, i.e., predictive of study endpoints while participation in the ABPM sub-study is an administrative stratification factor intended solely to ensure a similar number of sub-study subjects in each of the two randomized groups. [Note: recruitment in the ABPM sub-study is closed in Amendment 4.]

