12.13.3.1. ABPM Quality Control Criteria

Subjects will need to wear the ABPM device for two 24-hour sessions during the study: at Week -4 or at any time up until 1 week prior to randomization (baseline ABPM) and then at Week 16. The ABPM device will be placed after the assessments for the main study have been completed. Subjects will be expected to wear the ABPM device for 24 hours at each session. The ABPM device will measure BP and heart rate every 30 minutes during both awake and asleep hours. The times the subject awakens and goes to sleep during this 24-hour period will be recorded.

For each session, the ABPM Quality Control (QC) criteria as defined in the Project Requirement Specification (PRS) for ABPM must be met. If these criteria are not met the ABPM may be repeated (see Section 12.13.3.3).

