12.13.5. Statistical Analysis

The primary sub-study estimand is to compare the treatment effect on change from baseline in 24 hour average SBP at end of sub-study, in all randomized sub-study subjects. The statistical model for analysis will be an ANCOVA with terms for treatment and baseline 24 hour average SBP. This model will provide a point estimate and two-sided 95% CI for the treatment effect and a one-sided p-value for the superiority

assessment. Superiority will be established if the p-value is <0.025 . The primary analysis population will be the ABPM sub-study-ITT population defined as randomized subjects who were also entered into the ABPM sub-study.

Given the nature of ABPM measurement, a high degree of dropout unrelated to randomized treatment is anticipated. The potential high level of missing data poses a challenge in the interpretation of the primary ABPM sub-study analysis. The reason for missing ABPM data will be examined to explore the impact of missing data on the sub-study primary efficacy conclusions. If the majority (defined as $\geq 70\%$) of the missing data is due to either subject unwillingness to repeat the ABPM procedure or due to an unevaluable reading, then data will be treated as missing at random and the primary analysis will be considered sufficient. Otherwise, a sensitivity analysis may be performed that will use multiple imputation from the active control arm to replace data from both treatment groups that was missing due to reasons other than subject unwillingness or unevaluable readings. Further supplementary analyses may include an ABPM per-protocol population (PP) analysis, utilizing all ABPM-ITT subjects who are not major protocol violators or who did not change BP medications during the sub-study. Further details of sensitivity and supplementary analyses will be described in the RAP.

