- ~~Incident— Any malfunction or deterioration in the characteristics and/or performance of the pre-filled syringe, as well as any inadequacy in the labeling or the instructions for use which, directly or indirectly, might lead to or might have led to the death of a patient/user/other persons or to a serious deterioration in their state of health.~~
- ~~Not all incidents lead to death or serious deterioration in health. The non-occurrence of such a result might have been due to other fortunate circumstances or to the intervention of health care personnel.~~

It is sufficient that:

- ~~an **incident** associated with a pre-filled syringe happened and~~
- ~~the **incident** was such that, if it occurred again, might lead to death or a serious deterioration in health.~~

~~A serious deterioration in state of health can include:~~

- ~~life threatening illness~~
- ~~permanent impairment of body function or permanent damage to a body structure~~
- ~~a condition necessitating medical or surgical intervention to prevent one of the above~~
- ~~fetal distress, fetal death or any congenital abnormality or birth defects~~

Examples of incidents

- ~~a patient, user, care giver or professional is injured as a result of failure or misuse of the pre-filled syringe~~
- ~~a patient's treatment is interrupted or compromised by failure of the pre-filled syringe~~
- ~~a patient's health deteriorates due to failure of the pre-filled syringe~~

Appendix 13; Section 12.13.2 objectives and endpoints; secondary objectives; typo 4 hour average SBP should read 24 hour average SBP.

 • To compare daprodustat to darbepoetin alfa on BP parameters in the ABPM per-protocol population 	
 • Change in: 
 • 24 hour average SBP • 24 hour average DBP • 24 hour average mean arterial pressure from Baseline to Week 28 within each treatment group
---	---

*Appendix 13; Section 12.13.3.3 Study Assessments; Week 28 Study Visit; sentence 2.
Wording change for clarity.*

The time of administration of study medication, before and while ~~on~~-wearing the ABPM device, will be recorded

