Men and women able to have children and sexually active, must use acceptable methods of birth control from 30 days prior to the first dose of randomized treatment and until completion of the Follow-up visit (4-6 weeks after the end of randomized treatment).

- Methods of birth control include, one highly reliable method (such as intrauterine device, sterilisation of one of the partners, hormonal birth control methods) plus one supplementary barrier method (such as condom, diaphragm) with a spermicide.
- Two barrier methods used in combination with spermicide, are considered as reliable contraception methods.

The study doctor will discuss with the subject the methods of birth control that should be used while he/she is in this study and will help the subject to select the methods that are appropriate for him/her.

12.16.3. Changes Resulting from Protocol Amendment 3

This is an amendment to the protocol amendment dated 2016-OCT-12.

This amendment applies to all countries.

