- Add clarifications as to how weight, blood pressure, and laboratory assessments are to be done for those transitioning to dialysis.
- Added reminder for the ordering of assessments for blood pressure and that the over-read of the Day 1 ECG is required to confirm eligibility.
- Updated PRO section to add healthcare resource utilization data being collected for completeness and updated endpoint labels for EQ-5D-5L & EQ-VAS.

- Changed timepoint for blinded data cut need for psychometric validation of the Chronic Kidney Disease-Anemia Questionnaire.
- Revised statistical section to change from two-sided testing at the 5% level to one-sided testing at the 2.5% level; to clarify progression of CKD endpoint population and analysis model and for secondary endpoints, to change significance levels to p-values; to correct the timepoint for various Patient Reported Outcomes; to add a more complete description of the adjustments to statistical model; and to add additional text regarding the interim analysis process.
- Added exploratory endpoints around Hgb variability, iron parameters, transfusions, and dose adjustment scheme.
- Edited Risk Assessment information to align with version 8 of the Investigator’s Brochure.
- Updated FSH level to confirm menopause.
- Provision for possible adjustment to the Dose Adjustment Algorithm triggers for Hgb values 7.5 g/dL to <9.5 g//dL based on the review of blinded instream aggregate Hgb data.
- Modified Time and Events Table 13 ‘Schedule of Assessments Year 1 to the End of Study for Subjects Transitioning to Dialysis’. Main changes include footnotes to remove Kt/V and URR measurement for daily HHD; more clarity around randomized treatment dispensing and compliance, including provisions for deferring dose changes till the next HD treatment; removed capture of rescue medications from unscheduled and early termination visits as rescue evaluation is triggered at scheduled visits; added footnote to clarify storage biomarkers to be collected except if not permitted by IRB/EC or refused by subject; and addition of Argentina only pregnancy requirement..
- Changes to ABPM sub-study to add atrial fibrillation/flutter screening, remove home BP monitoring, change in time-point for assessment (from Week 28 to Week 16), and adjustments to objectives, endpoints and analysis.
- Clarified additional inclusion and added additional eligible visits to collect PK samples in PK sub-studies.

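### The footnote that dates the ABPM primary endpoint names Amendment 2, but the move from Week 28 to Week 16 was made in Amendment 3, so the Week 28 clause covers nobody by document date

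*Protocol*

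**What the plan says.** The primary ABPM endpoint in Section 12.13.2 is "Change in 24 hour average SBP from baseline to end of sub-study", compared between arms. Its end point is set by footnote 1: "The end of the sub-study is defined as Week 16, or Week 28 for subjects completing the sub-study prior to Amendment 2". The same footnote governs most of the secondary endpoints and both exploratory ones. In the current text the second ABPM session is placed by Section 12.13.3.1 at Week 16 ("and then at Week 16"), with no other post-baseline session.

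The protocol's history dates the change. The summary for Amendment 3 (Section 12.16.3.1) lists "change in time-point for assessment (from Week 28 to Week 16"). Amendment 3 is dated 5 October 2017 in the revision chronology and describes its predecessor thus: "This is an amendment to the protocol amendment dated 2016-OCT-12". That date is Amendment 2's. The list of specific changes for Amendment 2 (Section 12.16.2.2) still carries Week 28 endpoints, for example "24 hour average mean arterial pressure from Baseline to Week 28 within each treatment group", and its version of Table 8 starts the ABPM at Week 28.

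On the model, Section 12.13.5 states: "The statistical model for analysis will be an ANCOVA with terms for treatment and baseline 24 hour average SBP". Section 4.1 says of the randomization strata: "Region and ESA use at study entry are stratification factors considered to be potentially prognostically important".

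**The concern.** The Week 28 clause is there to keep the readings of subjects who were measured before the schedule changed. To do that, it has to refer to the amendment that changed the schedule. It refers to the one before it, under which Week 28 was still the rule.

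The footnote is current text and defines a primary endpoint. The amendment history is used here only to date the change, so this is not a mismatch between a log and superseded wording.

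At stake is whether Week 28 readings taken under the original protocol or Amendment 2 meet the protocol's own definition of the primary endpoint. Recruitment to the sub-study is closed, so subjects without a qualifying reading cannot be replaced. The design also has little power to spare.

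**Working it through.** **1. Dates.** Original protocol 9 June 2016 (Section 12.16.2); Amendment 2, 12 October 2016 (Section 12.16.3); Amendment 3, 5 October 2017 (revision chronology). Screening plus run-in lasts 7 to 9 weeks and the Week 28 visit window is ±1 week (Section 7).

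- Original protocol to Amendment 2: 125 days = 125/7 = 17.9 weeks, which is less than 28.
- Randomization on the protocol date itself, plus 28 weeks, gives 22 December 2016, about 10.1 weeks after Amendment 2.
- Shortest screening (7 weeks) plus an early Week 28 visit (27 weeks) gives 9 June 2016 + 34 weeks = 2 February 2017, about 16.1 weeks after Amendment 2.
- Amendment 2 to Amendment 3: 358 days = 51.1 weeks, during which Week 28 was the only scheduled post-baseline ABPM.

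So by document date the Week 28 clause is empty.

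**2. Subjects caught in transition.** A subject randomized after 5 October 2017 − 28 weeks = 23 March 2017 had not reached Week 28 when Amendment 3 was issued. A subject randomized before 5 October 2017 − 16 weeks = 15 June 2017 had already passed Week 16. Those randomized between the two dates had missed Week 16 and had not completed Week 28. Changing the footnote only to 'prior to Amendment 3' would leave them without a defined visit. Later adoption of the amendment at a site would move this window.

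**3. The plan's own sample size.** Inputs from Section 12.13.4: difference 6 mmHg, SD 11 mmHg, one-sided 2.5%, 80% power, 20% withdrawal, 68 per group.

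- n = 2(1.960 + 0.842)² × 11²/6² = 52.8, so 53 evaluable per group; 53/0.8 = 66.3, so 67. The stated 68 is consistent.
- Evaluable per group: 68 × 0.8 = 54.4. Power is 80.5% by noncentral t and 81.2% by the normal approximation.
- Smallest observed difference that reaches significance, 54 per group: t(0.975, 106) × 11 × √(2/54) = 4.20 mmHg, matching the stated 4.2. This is a significance threshold; the effect the sub-study is powered to detect is 6 mmHg.

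**4. Illustration only: if Week 28 readings were not used.** The fraction affected is assumed. The last column also assumes that baseline SBP explains 10% of the variance of change, because the planned model adjusts for baseline.

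| Assumed loss of evaluable subjects | Power, no covariate | Power, baseline R² = 0.10 |
|---|---|---|
| 0% | 80.5% | 84.4% |
| 5% | 78% | 82.5% |
| 10% | 76% | 80.4% |
| 20% | 71% | 75.5% |

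**5. Region in the model (separate, minor).** With 5 degrees of freedom spent and an assumed share of residual variance explained by region of 0, 0.02 or 0.05, power is 80.5%, 81.2% or 82.4%, against 80.5% without it: a gain of 0 to 2 points.

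**The case against.** The strongest reply is that the intent is plain. The footnote exists to keep Week 28 readings, and nothing in the protocol directs that any be discarded. Section 12.13.5 sends further statistical detail to the RAP, which is not shown here and could map these visits sensibly. This stands. A reader might infer from the footnote that subjects measured at Week 28 lose their endpoint. The document supports only the narrower statement that a literal reading assigns them a visit at which no ABPM was scheduled.

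Second, the number affected is unknown. The protocol gives no first-randomization date and no count of Week 28 ABPMs, so it may be small or zero. A reader might infer that power drops below 80%. That needs both an assumed fraction lost and an analysis without the baseline covariate; under one modest assumption about baseline, power stays above 80% up to a 10% loss. This stands too.

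Third, if 'prior to Amendment 2' meant adoption at the site, a lag of about 16 weeks or more could let someone qualify. That is possible, but the cut-off would still be wrong, because Week 28 also applied under Amendment 2.

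Fourth, omitting region is a modelling choice unrelated to the footnote. It does not bias the treatment estimate; at most the standard error is somewhat larger than it need be. This is accepted, and the point is kept only as a minor addition.

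**Conclusion.** The wrong amendment number is established from the protocol's own text and dates. By document date the Week 28 clause covers no subject, and the subjects it was meant to cover fall under the Week 16 definition. The consequence is a defect in the definition of the sub-study's primary endpoint. It is not a demonstrated loss of data: the loss could be anywhere from none upward, and the power figures above rest on assumed fractions. Neither co-primary endpoint of the main study is affected, and the stated sample size and power of the sub-study reproduce.

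It still merits correction in the protocol. Using Week 28 readings for these subjects through the RAP alone would depart from the written definition and could be questioned as a choice made after data existed. The region term is optional and worth about 0 to 2 points of power, if region explains 0 to 5% of residual variance.

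**What to change.** Reword footnote 1 so that the end of the sub-study is Week 16, or Week 28 for subjects whose closing ABPM was scheduled at Week 28 under the protocol version in force for them (before Amendment 3). Add a sentence stating which visit applies to subjects already past Week 16 but short of Week 28 when Amendment 3 took effect, that is, those randomized from about 23 March to 15 June 2017. Swapping the number 2 for 3 is not enough, because it leaves this group undefined. Report in the RAP how many subjects fall under each visit.

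The cost is two sentences in the protocol, with no change to sample size, conduct or recruitment. Optionally, add region to the sub-study ANCOVA at a cost of a few degrees of freedom out of about 107. A term for assessment visit (Week 16 or Week 28) is a matter of preference.
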